8.2. Handling Partial or Missing Dates on AE, CM, and MH

Partial or complete missing date for AEs, concomitant medication (CM), and medical history (MH) will not be imputed. TEAE and prior and concomitant medication will be determined by using available date information. If available date information cannot determine, refer to section 7.1 for prior and concomitant medication, section 7.4 for TEAE.

9. CHANGES TO PLANNED ANALYSES

The EN3835-202 protocol [Section 17.2] defines the 4 different cohorts and states all efficacy and safety analyses will be done within the classified cohort. In this statistical analysis plan, the efficacy and safety analyses are summarized by different phases (observation phase, treatment phase, long-term durability visits) and populations (observation population, safety population, effectiveness population, and durability population) instead.

The EN3835-202 protocol [Section 17.2.1] defines the observational population as including all subjects rolled over from the EN3835-201 study who do not receive any treatment in the current study. This population is renamed to “Observation Population” for this document, as described in section 2. It is defined as: The observation population includes all subjects rolled over from the EN3835-201 study. The cellulite assessment evaluations and safety analyses for the data collected from Screening A to Day 360 will be based on this population. This change will allow the data observed during observation phase to be summarized under this new population.

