12.1.4. Treatment Assessments (Optional)

After unblinding of treatment assignment in the EN3835-201 study, subjects are eligible for optional treatment in the open-label study, provided they meet the inclusion and exclusion criteria detailed in section [11](#) and at least 1 quadrant meets the criteria for treatment. A subject may receive a maximum of 2 courses of treatment (6 treatment sessions) overall (total of treatments in double-blind and open-label study). If a subject received placebo in the double-blind study, she may be eligible for 2 treatment courses in the open-label study; if a subject received active drug in the double-blind study, she may be eligible for 1 additional treatment course (3 treatment sessions) in the open-label study.

Selection of Treatment Quadrant

During the Screening B visit, each subject will have photographs taken of the 4 targeted quadrants of the study (eg, their left and right buttocks and left and right posterolateral thighs). Subjects will receive instructions ([Appendix D](#)) for using the PR-PCSS and will use the scale to rate the severity of their cellulite in each of the 4 quadrants by comparing each of their digital image photographs with the PR-PCSS instrument. This self-assessment will take place in a private setting to minimize any potential bias from site personnel. The Investigator will then assess each of the subject's 4 quadrants live in real-time using the CR-PCSS. The Investigator will then examine each of the 4 quadrants live to assess the subject using the Hexsel CSS as described in section [13.1.1.6.\(12\)](#) Subjects must have at least 1 quadrant that meets the following criteria for treatment in the study:

1. PR-PCSS score of 3 or 4, and
2. CR-PCSS score of 3 or 4, and
3. Hexsel CSS score no greater than 13.

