17.2. Subject Cohorts and Subject Populations

Subjects will be classified into 1 of 4 different cohorts depending on where they receive the treatment of EN3835 in relation to where they received treatment in study EN3835-201. The 4 cohorts are:

1. Observational subjects only - subjects who received EN3835 in study EN3835-201 but do not receive any injections in the current study
2. Re-treatment subjects - subjects who received EN3835 in study EN3835-201 and receive EN3835 in the current study in the same quadrant that was treated in the EN3835-201 study. This will only be allowed for subjects who have baseline severity ratings in the current study at or worse than the baseline seen in study EN3835-201 for both the CR-PCSS and PR-PCSS of the quadrant.
3. Re-dosing subjects - subjects who received EN3835 in study EN3835-201 and receive EN3835 in the current study in a quadrant different than the EN3835-treated quadrant in study EN3835-201.
4. Initial treatment subjects - subjects who received placebo in study EN3835-201 and receive EN3835 in the current study.

All efficacy and safety analyses will be done within the classified cohort. Durability of treatment effects defined as the time from onset of change from baseline of PR-PCSS and CR-PCSS in the quadrant treated in study EN3835-201 until the time that the treated quadrant return to baseline cellulite severity ratings of PR-PCSS and CR-PCSS in an EN3835-treated quadrant will be determined for all subjects that were treated with EN3835 in either this study or study EN3835-201.

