1.3.2. Secondary Objectives

The secondary objectives of this study are:

- To evaluate safety and immunogenicity of re-treating or re-dosing a subject that had previously received treatment with EN3835
- To evaluate the durability of response to EN3835 in EFP severity over the 12-month post initial dosing of EN3835 in subjects previously receiving active treatment in study EN3835-201 using the PR-PCSS and the CR-PCSS
- To evaluate the durability of response to EN3835 in EFP severity beyond 12-month post initial dosing of EN3835 in subjects previously receiving active treatment in study EN3835-201 using the PR-PCSS and the CR-PCSS
- To evaluate long-term response to EN3835 in assessments of EFP including subject satisfaction, Investigator Global Aesthetic Improvement Scale (I-GAIS), and Subject Global Aesthetic Improvement Scale (S-GAIS)
- To assess cellulite severity assessments in quadrants treated in this study with EN3835
- To evaluate immunogenicity after exposure to EN3835

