2. ANALYSIS POPULATIONS AND PHASES

The following populations will be considered in the statistical analysis of the study:

- Observation Population: The Observation population includes all subjects rolled over from study EN3835-201. The cellulite assessment evaluations and safety analyses on data collected during observation phase will be performed using this population.
- Safety Population: The Safety population will include all subjects who receive at least 1 dose of EN3835 in the current study. All safety analyses for the treatment phase will be performed using this population. For by region summaries, safety population is considered within each treatment course.
- Effectiveness Population: The Effectiveness population includes all safety subjects who have a baseline and at least 1 post-baseline assessment on both the CR-PCSS and PR-PCSS on the quadrant selected for treatment in the current study. All analysis of effectiveness for the treatment phase will be based on this population. For by region summaries, effectiveness population is considered within each treatment course.
- Durability Population: This population is defined as all active responders who have both CR-PCSS and PR-PCSS at 180 days or above. The active responders are subjects treated with EN3835 with improvements of at least 1 level on each

scale (CR-PCSS and PR-PCSS) at Day 71 visit compared to the baseline. Analysis of durability of treatment effect will be performed using this population.

- Durability Population for Double-blind Treated Subjects: This population is defined as all subjects in the durability population who showed an improvement of at least 1 level on each scale (CR-PCSS and PR-PCSS) at Day 71 visit compared to the baseline for the quadrant treated with EN3835 in double-blind study EN3835-201.
- Durability Population for Open-label Treated Subjects: This population is defined as all subjects in the durability population who showed an improvement of at least 1 level on each scale (CR-PCSS and PR-PCSS) at Day 71 visit compared to the baseline for the quadrant treated with EN3835 in the open-label study EN3835-202 study, who did not have the same quadrant treated with EN3835 in double-blind study EN3835-201. For by region summaries, this population is considered within each treatment course.

The following 2 phases will be summarized in the statistical analysis of the study:

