7.4. Adverse Events

Treatment-emergent adverse events (TEAEs) is defined as any AE with onset date on or after the treatment start date in each treatment course in study EN3835-202. TEAEs are defined within each treatment course in study EN3835-202. AEs with missing or partial onset date and cannot be determined in which treatment course it occurred with its onset and end dates will be considered as TEAEs in treatment course 1. AEs with missing or partial onset date and cannot be determined in which treatment session it occurred with its onset and end dates will be considered as earliest treatment course and earliest treatment session possible.

Treatment-related adverse events are TEAEs with a relationship to study medication of possible, probable, or missing.

AEs will be coded using the Medical Dictionary for Regulatory Activities (MedDRA), Version 19.0.

Overall AE summaries for observation phase as well as overall TEAE summaries for treatment phase will be tabulated. Descriptive statistics (the number and percentage) for subjects reporting AEs, TEAEs, and Adverse Events of Special Interest (AESI) will be tabulated by system organ class (SOC) and preferred term (PT); by SOC, PT, and severity; and by SOC, PT, severity and relationship to study drug. TEAE will also be summarized by SOC, PT, and treatment course. The duration of treatment related AE descriptive statistics will be summarized within each PT under each SOC. The TEAE tables will be sorted by SOC and PT in decreasing frequency of the number of subjects in the overall column.

If there are more than 1 AE coded to the same SOC or PT for the same subject under a certain column in the summary table, the subject will be counted only once for that SOC or PT under that column. If there are more than 1 AE coded to the same PT for the same subject, the subject will be counted only once for that PT using the most severe and most related occurrence for the summarization by severity and by relationship to the study drug. If there are more than 1 AE coded to the same PT, the longest AE will be used for that PT for the duration descriptive statistics.

Serious adverse events (SAEs) and AEs leading to premature discontinuation of study drug will be summarized. Listings will be presented for subjects with AEs, SAEs, AESI, AEs leading to discontinuation, and subjects who die (if any).

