7.7. Immunogenicity Analyses

Immunogenicity variables include anti-AUX-I/anti-AUX-II binding antibody results. Binding antibody levels will be determined from samples collected on Day 1 Day 71 and Day 360.

Descriptive statistics (percent of positive measurements and average antibody level) will be presented for anti-AUX-I and anti-AUX-II antibody levels at each time point by region treated, treatment course and overall. Average antibody levels will be summarized on logarithmically transposed titer values.

In addition, a subset of these immunogenicity samples will be analyzed for neutralizing antibodies by calculating the frequency count of the positive samples and the negative samples and the percentage of samples in each category.

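### SAP 9 drops the protocol cohorts, so no planned safety or antibody table reports re-exposure in women given EN3835 in study 201, or separates re-treatment from re-dosing

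*Combined protocol and SAP*

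**What the plan says.** Protocol 17.2 (Amendment 2 text) defines four cohorts: observational, re-treatment, re-dosing and initial treatment. It then states: "All efficacy and safety analyses will be done within the classified cohort". SAP 9 records a departure: "In this statistical analysis plan, the efficacy and safety analyses are summarized by different phases". SAP 9 gives a reason for redefining the observation population, but none for dropping the cohorts.

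The first secondary objective in SAP 1.3.2 is unchanged: "To evaluate safety and immunogenicity of re-treating or re-dosing a subject that had previously received treatment with EN3835".

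The treatment phase is reported as follows.

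- **Safety population (SAP 2).** "The Safety population will include all subjects who receive at least 1 dose of EN3835 in the current study", whichever arm they had in study 201.
- **Adverse events (SAP 7.4).** "TEAE will also be summarized by SOC, PT, and treatment course". Course is counted inside the extension: "TEAEs are defined within each treatment course in study EN3835-202".
- **Antibodies (SAP 7.7).** Binding antibodies are shown "at each time point by region treated, treatment course and overall". No split is stated for neutralizing antibodies.
- **Exposure and compliance (SAP 7.2, 7.3).** By region, session and 202 course.
- **Vital signs and laboratory values (SAP 7.5, 7.6).** No split by course or prior exposure is stated.
- **Effectiveness (SAP 6.2.1, 6.2.2).** By treated quadrant or region and study day, with treatment course mentioned in 6.2.2 as a possible exception.

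A split by 201 arm is stated only for the observation endpoints of the quadrant treated in study 201 (SAP 6.2.3).

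Protocol 12.1.4 caps EN3835 at two courses over both studies. A woman who received placebo in 201 may have two courses in 202. Of a woman who received active drug it says "she may be eligible for 1 additional treatment course (3 treatment sessions) in the open-label study".

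**The concern.** EN3835 is a foreign protein, and protocol 12.1.4.2 requires sites to be ready for allergic reactions. Repeat exposure is one of the stated reasons for the study (protocol 8.6 and 10.4). The questions are whether a second course brings different reactions or antibody levels, and whether it matters if the second course goes into the same quadrant or a new one.

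The course number within study 202 does not identify a second exposure. For a former placebo woman, course 1 is her first contact with the drug. For a former active woman, course 1 is her second. A rate in the course 1 or overall column is therefore a weighted average of two different situations. The weights depend on how many women of each kind chose treatment.

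**Working it through.** **1. The plan's own figure.** Protocol 17.1: 0.95 × 350 = 332.5, rounded up to 333, which reproduces. Study 201 was randomized 1:1 (protocol 8.3.1.4), so with equal rollover 333 / 2 = 166.5, about 166 women come from each former arm. SAP 1.7 gives approximately 350 instead; this does not affect the point.

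**2. Who can fall in which column.** Under the two-course cap:

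| Study 201 arm | Course in 202 | EN3835 exposure | Protocol 12.1.4 label | SAP column |
|---|---|---|---|---|
| Placebo | First | First ever | Treatment | Course 1 |
| Active | First and only | Second | Re-treatment or re-dosing | Course 1 |
| Placebo | Second | Second | Re-treatment or re-dosing | Course 2 |

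Course 1 is mixed, course 2 is purely re-exposure, and the overall column is mixed. No column separates same from different quadrant. A split by treated quadrant gives the anatomical site, not whether that site had EN3835 before.

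**3. Share of re-exposures in course 1.** The documents give no uptake. I assume 60% to 100% of former placebo women and 25% to 100% of former active women choose treatment. Share s = (former active treated) / (all treated in course 1).

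- All choose treatment: 166 / 332 = 0.50.
- Placebo 100%, active 25%: 42 / 208 = 0.20.
- Placebo 60%, active 100%: 166 / 266 = 0.62.

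**4. What course 1 would show.** Pooled rate = (1 − s) × p_first + s × p_re. All rates below are assumed.

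| s | Event risk 1% first, 5% re-exposed | Pre-dose antibody positivity 5% naive, 95% pre-exposed |
|---|---|---|
| 0.20 | 1.8% | 23% |
| 0.50 | 3.0% | 50% |
| 0.62 | 3.5% | 61% |

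In the other direction, suppose course 1 shows 4% and s = 0.50. Then p_re = (0.04 − 0.50 × p_first) / 0.50 = 0.08 − p_first, which can lie anywhere from 0% to 8%. At s = 0.20 the upper end is 0.04 / 0.20 = 20%.

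**5. Comparing course 2 with course 1.** If re-exposure risk is the same in both former arms, course 2 minus course 1 equals (1 − s) × (p_re − p_first). At s = 0.50 with 1% and 5%, the table shows 5% − 3% = 2 points where the true difference is 4.

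**6. What course 2 can still show.** It has at most about 166 women, or 100 at 60% uptake, if all of these also take a second course. With zero events, the one-sided 95% upper limit is 1 − 0.05^(1/n), which is 1.8% at n = 166 and 3.0% at n = 100. That describes re-exposure in former placebo women only.

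**The case against.** Several counter-arguments have force.

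- **Course 2 is clean.** A reader might infer that every treatment-phase percentage mixes naive and pre-exposed women. The documents do not support that: course 2 contains only second exposures, and adverse events and binding antibodies are planned by course. This stands. But course 2 omits all former active women, who are the whole of the protocol 17.2 re-treatment and re-dosing cohorts, and it pools re-treatment with re-dosing. Its entry rules also differ. Former active women need a return to their 201 baseline severity before re-treatment, whereas a former placebo woman's second course in the same quadrant needs only the general criteria.
- **The data exist.** A reader might infer that the objective cannot be answered at all. It can: 201 arm and treated quadrant are recorded, and SAP 7.4 plans listings of adverse events. What is missing is a tabulation.
- **The objective is about safety and immunogenicity.** It does not mention effect. This stands. The case for changing SAP 6.2.1 and 6.2.2 rests on protocol 17.2 alone.
- **The protocol is not a clean standard either.** Restoring the 17.2 cohorts literally would leave former placebo women's second courses under initial treatment, while 12.1.4 assigns them to re-treatment or re-dosing. Protocol 17.7 plans antibodies by region and overall, so adding course is a step forward. Both points stand and shape the fix.
- **The study is descriptive, uncontrolled and self-selected, and SAP 9 declares the change openly.** True; no test or decision rule is affected. A descriptive study still has to describe the groups its objective names.

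**Conclusion.** The concern holds, within limits. SAP 9 removes the protocol's analysis by cohort while SAP 1.3.2 keeps the objective those cohorts served. No planned safety or antibody table answers that objective for women treated with EN3835 in study 201, and none separates re-treatment from re-dosing. Re-exposure as a whole is described only in former placebo women, through course 2.

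That course 1 and the overall columns are mixed follows from the two-course cap and needs no assumption beyond some women of each former arm choosing treatment. The size is uncertain. The 20% to 62% share rests on assumed uptake, and the event and antibody rates are illustrations, because the documents give none. They show how little a pooled rate says about re-exposure; they do not predict what the trial will find.

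**What to change.** In SAP 7.2 to 7.7, and in 6.2.1 and 6.2.2 to honour protocol 17.2, classify each 202 course by the woman's cumulative EN3835 course number over both studies and by whether the quadrant is the same as the one that previously received EN3835. A quadrant that received only placebo in 201 does not count as previously treated. Add these columns:

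1. Initial exposure: former placebo women, first course.
2. Re-dosing: second EN3835 course, different quadrant.
3. Re-treatment: second EN3835 course, same quadrant.
4. All re-exposed: columns 2 and 3 together.

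Former placebo women's second courses go in column 2 or 3, as in protocol 12.1.4. Three rules should be written in:

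- **Region.** Keep the split by region that protocol 17.7 specifies; the new columns are additions.
- **Pre-dose antibody value.** Footnote m of SAP Table 3 omits the Day 1 sample when that visit coincides with Day 71 of the prior course. State that the Day 71 sample is then the pre-dose value.
- **Women with two 202 courses.** Count data collected after the second course starts, including a later Day 360 antibody sample, under the re-exposure column and not under initial exposure.

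SAP 9 should also say which tables serve the re-treating and re-dosing objective. The cost is SAP wording, more table columns and small cells, mainly for re-treatment. Small cells are best shown as counts with intervals. No new data are needed.

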APPENDIX A. PCI CRITERIA

Laboratory Values

Test	Low	High
Platelets ($10^9/L$)	≤ 100	≥ 650
Hemoglobin (g/L)	≤ 100	≥ 190
Hematocrit	≤ 0.3	≥ 0.6
ALT	---	$\geq 3 \times ULN$
AST	---	$\geq 3 \times ULN$
Creatinine ($\mu\text{mol}/L$)	---	≥ 300
BUN (mmol/L)	---	≥ 12

Vital Signs

Test	Low	High
Systolic Blood Pressure	≤ 90 mmHg and decrease ≥ 20 mmHg from baseline	≥ 180 mmHg and increase ≥ 20 mmHg from baseline
Diastolic Blood Pressure	≤ 50 mmHg and decrease ≥ 15 mmHg from baseline	≥ 105 mmHg and increase ≥ 15 mmHg from baseline
Pulse Rate	≤ 50 bpm and decrease ≥ 15 bpm from baseline	≥ 120 bpm and increase ≥ 15 bpm from baseline
Respiratory Rate	≤ 8 brpm and decrease ≥ 7 brpm from baseline	≥ 25 brpm and increase ≥ 7 brpm from baseline
Temperature	---	$\geq 38.3^\circ\text{C}$ and increase $\geq 1.1^\circ\text{C}$ from baseline
